Comparison of the ID NOW and Accula Point-of-Care Assays for the Detection of SARS-CoV-2

[name]. D (ABMM)
Ascension Michigan Laboratory Services
Clinical Microbiology Laboratory

Background:

In December 2019, a novel coronavirus was found to cause respiratory infections in Wuhan Province, China. The virus rapidly spread throughout Wuhan Province, then to other parts of China and eventually the world. The illness ranged from asymptomatic carriers to acute respiratory distress (ARDS). The virus was subsequently named SARS-CoV-2 and the respiratory disease, coronavirus disease-2019 (COVID-2019). In March 2020 the World Health Organization (WHO) classified COVID-2019 as a pandemic (4).

In response to the pandemic, the Food and Drug Administration (FDA) approved several platforms under emergency use authorization (EUA). These platforms do not have full FDA approval and may be used for COVID-19 testing temporarily in a clinical laboratory until the manufacturer receives full FDA clearance for use in the U.S (3).

Two point of care (POC) platforms with current EUA approval are the ID NOW COVID-19 (Abbott) and the Accula SARS-CoV-2 tests (Mesa Biotech) (1,2). Both tests are designated as CLIA waived complexity. POC's play a vital role in the diagnosis of COVID-19, especially in laboratories and clinics where testing including molecular assays and serology is not available.

The ID NOW COVID-19 test is an automated qualitative assay that is EUA approved for use on nasal, nasopharyngeal (NP), and oropharyngeal specimens (2). This assay utilizes isothermal nucleic acid amplification technology for the qualitative detection of SARS-CoV-2 viral nucleic acids within 15 minutes. The Accula SARS-CoV-2 test is also a qualitative assay and is approved for use on nasal specimens. The test uses reverse-transcription polymerase chain reaction followed by lateral flow and provides results within 30 minutes.

Currently the Clinical Microbiology Laboratory at Ascension Michigan Laboratory Services has validated and utilizes the ID NOW COVID-19 assay to analyze Ascension St. John (ASJ) emergency department (ED) and inpatient specimens. While this assay has a high positive predictive value, the sensitivity and negative predictive value are low. Furthermore, acquisition of test kits is limited due to large demand and limited supplies.

Purpose:

The purpose of this study is to compare SARS-CoV-2 results from clinical specimens on the ID NOW and the Accula systems. If the Accula system is comparable or demonstrates superior test parameters including sensitivity, then this assay may potentially be used throughout Ascension, especially in markets which have limited access to testing. This in turn will assist in improving turnaround times for COVID-19 results and facilitate reinstating elective surgeries.

Methods:

All testing will be conducted in a College of American Pathologists (CAP)- accredited biosafety level-2 laboratory with restricted access. All patient specimens will be manipulated under a certified biosafety level-2 cabinet.

The testing personnel for the ID NOW will be medical laboratory technologists and technicians in the clinical microbiology laboratory who have previously been trained and are competent under Clinical Laboratory Improvement Amendments (CLIA) guidelines at performing the ID NOW COVID-19 assay. Testing personnel for the Accula assay will consist of a lead medical laboratory scientist and the technical director of the microbiology laboratory, a Ph.D. level scientist.

The ASJ microbiology laboratory validated the ID NOW COVID-19 assay in April 2020. The protocol for testing is located on PolicyStat and can be accessed using the link below. https://ascension-lab.policystat.com/policy/7897941/latest/. Currently when rapid COVID-19 tests are ordered on ASJ ED patients or inpatients one nasal swab is collected by the clinical staff. The swab is then placed in a sterile conical tube and delivered to the microbiology laboratory where the COVID-19 test is run STAT on the ID NOW. Specimens used for ID NOW testing cannot be re-used for repeat ID NOW testing or any other laboratory testing due to the initial genomic extraction step which requires use of the entire swab.

Patients with orders for rapid COVID-19 testing who have consented to participate will be included in the study. We will also include patients who have been confirmed positive for COVID-19 by PCR, swabs will be collected from these patients after obtaining consent. For patients with orders for rapid COVID-19 testing, one additional clinical specimen, anasal specimen will be collected from the patient at the same time as the initial specimen for the ID NOW. For patients who were confirmed positive by PCR, two additional swabs will be collected: one for the ID NOW and one for the Accula test. Swabs for both ID NOW and Accula testing will be provided to the clinical teams in pre-packaged kits with directions on specimen collection and transport. After collection, all swabs must be labeled with a specimen label (per current protocol). Following consent and collection of specimens, specimens will be sent to the microbiology laboratory. The ID NOW COVID-19 assay will continue to be performed STAT.

If laboratory testing personnel are available, the additional swab will be eluted in a buffer tube as recommended by the manufacturer and then utilized for the Accula SARS-CoV-2 assay. In the event that immediate testing cannot be performed, however, swabs will be stored at room

temperature for two hours or 2-8°C for up to 24 hours prior to testing on the Accula (per manufacturer's guidelines). The Accula system is a new platform for the microbiology laboratory. The manufacturer of the Accula Test, Mesa Biotech, has been working in conjunction with the National Ascension Laboratory team to pilot this study in two Ascension Markets (Michigan and Florida). Five Accula analyzers will be sent to the Ascension Michigan Clinical Microbiology Laboratory along with SARS-CoV-2 test kits. The protocol for testing will strictly follow the manufacturer's instructions (https://www.fda.gov/media/136355/download).

If there is a discrepancy between the ID NOW and Accula test results, an additional specimen (nasal) will be collected from the patient, if possible (i.e. if the patient remains in-house) to confirm the COVID-19 results (unless the PCR results are already available). This additional test must be more sensitive than POCs. If the ASJ molecular laboratory is able to complete validation on the Roche 8800 which will be arriving on April 24, 2020, the additional specimen will be run with the Roche COVID-19 assay. If not, specimens will be sent out to a reference laboratory for confirmation COVID-19 testing.

This study will evaluate accuracy (correlation) by comparing Accula results to the ID NOW, precision (reproducibility) by repeating select specimens with different users and on different analyzers, limit of detection by diluting commercial SARS-CoV-2 controls with a known concentration and cross-reactivity by testing known respiratory viruses (including influenza A, B and RSV) on the Accula.

Data Management and Analysis:

The electronic data from this study will be stored on the Ascension network which is a password-protected encrypted computer drive. All HIPAA guidelines will be followed to protect patient information. Only the lead technologist and technical director will have access to this file.

Currently, patient results from the ID NOW test are entered in the laboratory information system (LIS) by microbiology staff. Since the ID NOW is not interfaced with the LIS, patient reports are printed prior to verification and the hardcopies are stored in a binder in the laboratory. As required by CAP, these documents are stored securely in the laboratory for two years.

The lead technologist or technical director will enter the ID NOW results into the secure data file using the ID NOW hardcopy reports. The results from the Accula test and the Roche or send-out test, if performed, will be entered into the same spreadsheet using the same barcode number as the ID NOW. The only patient demographic information that will be recorded in the spreadsheet is the specimen barcode number for the ID NOW.

Any subsequent data shared with individuals other than the study testing personnel will not contain any patient identifiers, including the specimen barcode used as the identifier in the data collection file.

The following test parameters for the Accula will be calculated using the ID NOW as a comparator: sensitivity, specificity, positive-predictive value, negative predictive value.

Sample Size and Duration of Study:

The aim is to test 100 unique patients. The duration of this study will be determined based upon the number of specimens collected daily. We anticipate that sufficient specimens will be collected within a one-week time period.

Predicted Results:

The Accula SARS-CoV-2 test parameters including sensitivity, specificity, positive-predictive value, and negative predictive value will be similar or superior to the ID NOW COVID-19 assay.

References:

- 1. Accula SARS-CoV-2 Test IFU (EUA). Mesa Biotech, 2020.
- 2. ID NOW COVID-19 Assay IFU (EUA). Abbott, 2020.
- 3. Interim Guidelines for Collecting, Handling, and Testing Clinical Specimens from Persons for Coronavirus Disease 2019 (COVID-19). CDC. Last accessed 20 April 2020.
 - https://www.cdc.gov/coronavirus/2019-ncov/lab/guidelines-clinical-specimens.html
- 4. Laboratory testing for 2019 novel coronavirus (2019-nCoV) in suspected human cases: Interim guidance. World Health Organization. 19 March 2020.

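### Known PCR-positive patients and rapid-order patients fall into one Accula-versus-ID NOW calculation, so all four parameters depend on an unstated recruitment mix

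*Combined protocol and SAP*

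**What the plan says.** The Methods section describes two routes into the study. The first is routine: "Patients with orders for rapid COVID-19 testing who have consented to participate will be included in the study". The second selects on disease status: "We will also include patients who have been confirmed positive for COVID-19 by PCR". Patients on the second route give two new swabs, one per assay, at an unstated interval after their PCR.

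Sample Size and Duration of Study gives one total, "The aim is to test 100 unique patients", with no split between the routes. Data Management and Analysis gives one analysis: "The following test parameters for the Accula will be calculated using the ID NOW as a comparator: sensitivity, specificity, positive-predictive value, negative predictive value". It describes no breakdown by route.

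Three other statements bear on this:

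- Background, on the comparator: "While this assay has a high positive predictive value, the sensitivity and negative predictive value are low".
- Methods, on discrepant pairs: a further specimen is taken, where possible, "to confirm the COVID-19 results (unless the PCR results are already available"). Nothing says that the confirmatory or existing PCR result enters the four parameters.
- Data Management and Analysis, on the data file: besides the ID NOW results and barcode, "The results from the Accula test and the Roche or send-out test, if performed, will be entered into the same spreadsheet". Neither the recruitment route nor the enrolling PCR result is listed.

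The Purpose section states the use: "If the Accula system is comparable or demonstrates superior test parameters including sensitivity, then this assay may potentially be used throughout Ascension". Predicted Results expects all four parameters to be similar or superior to those of ID NOW.

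**The concern.** The two groups answer different questions. Rapid-order patients have unknown status and resemble those in whom the assay would be used. Patients on the second route are all known to have tested PCR positive, so none was enrolled as uninfected, and they are swabbed some time after diagnosis rather than at presentation.

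Pooling them has two effects. First, PPV and NPV depend on the proportion infected, which recruitment now sets. Second, because the comparator misses infections, apparent specificity depends on the mix too. A PCR-confirmed patient who is ID NOW negative and Accula positive enters the calculation as an Accula false positive, although the study already holds a positive PCR for that patient. The more infections Accula finds that ID NOW misses, the worse its apparent specificity becomes.

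At stake is whether the four parameters can inform wider use of Accula. A reader could not tell how much of any figure came from the assay and how much from who was recruited.

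**Working it through.** **The plan's own figure.** The target of 100 cannot be reproduced: the plan gives no prevalence, cohort split, margin, power or precision target. The check therefore asks how far the four parameters move when only the recruitment mix changes.

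**Inputs.** From the plan: 100 patients, two groups, ID NOW as comparator, ID NOW sensitivity low (no figure given). Assumed for illustration: ID NOW sensitivity seI = 0.75, specificity 0.99; Accula sensitivity seA = 0.90, specificity 0.98; prevalence 10% among rapid-order patients; errors independent given infection status; k = 0, 10, 30 or 50 known positives in 100.

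**Probability of each result pair (ID NOW/Accula).**

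- Infected: +/+ 0.75 × 0.90 = 0.675; +/− 0.75 × 0.10 = 0.075; −/+ 0.25 × 0.90 = 0.225; −/− 0.25 × 0.10 = 0.025.
- Uninfected: +/+ 0.01 × 0.02 = 0.0002; +/− 0.01 × 0.98 = 0.0098; −/+ 0.99 × 0.02 = 0.0198; −/− 0.99 × 0.98 = 0.9702.

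Let a, b, c, d be the expected counts of +/+, +/−, −/+ and −/−. Against ID NOW, sensitivity = a/(a+b), specificity = d/(c+d), PPV = a/(a+c), NPV = d/(b+d).

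**k = 0** (10 infected, 90 uninfected):

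- a = 6.750 + 0.018 = 6.768
- b = 0.750 + 0.882 = 1.632
- c = 2.250 + 1.782 = 4.032
- d = 0.250 + 87.318 = 87.568
- Specificity = 87.568/91.600 = 95.6%

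**k = 50** (50 known positives, 5 infected and 45 uninfected rapid-order patients):

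- a = 33.750 + 3.375 + 0.009 = 37.134
- b = 3.750 + 0.375 + 0.441 = 4.566
- c = 11.250 + 1.125 + 0.891 = 13.266
- d = 1.250 + 0.125 + 43.659 = 45.034
- Specificity = 45.034/58.300 = 77.2%

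| Known positives per 100 | Sensitivity | Specificity | PPV | NPV |
|---|---|---|---|---|
| 0 | 80.6% | 95.6% | 62.7% | 98.2% |
| 10 | 85.3% | 93.1% | 68.6% | 97.3% |
| 30 | 88.0% | 86.6% | 72.3% | 94.8% |
| 50 | 89.1% | 77.2% | 73.7% | 90.8% |

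At k = 50, 11.25 of the 13.27 expected Accula false positives (85%) are PCR-confirmed patients. At k = 30 it is 6.75 of 9.57 (71%).

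**Sensitivity checks, k = 0 to k = 50.** Under maximal dependence, Accula detects every infection that ID NOW detects; this adds 0.75 − 0.675 = 0.075 to the infected +/+ and −/− probabilities and takes it from the other two.

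| Change to the assumptions | Sensitivity | Specificity | PPV | NPV |
|---|---|---|---|---|
| In known positives, sensitivity 50% ID NOW, 80% Accula | 80.6 to 80.1% | 95.6 to 68.9% | 62.7 to 51.5% | 98.2 to 89.3% |
| Maximal dependence | 89.5 to 98.9% | 96.4 to 84.3% | 69.6 to 81.9% | 99.0 to 99.1% |
| Rapid-order prevalence 30% | 87.3 to 89.4% | 89.4 to 69.9% | 71.4 to 74.1% | 95.9 to 87.2% |
| ID NOW sensitivity 60% | 78.5 to 88.8% | 94.2 to 68.9% | 50.2 to 58.9% | 98.3 to 92.5% |
| ID NOW sensitivity 95% | 82.4 to 89.2% | 97.5 to 92.9% | 79.3 to 93.3% | 97.9 to 88.6% |

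**A second set of assumptions** (Accula 90% and 99%, ID NOW 80% and 99%, prevalence 20%), with the known-positive share rising from 0 to 75%: sensitivity 85.8 to 89.7%, specificity 94.7 to 59.2%, PPV 76.6 to 79.8%, NPV 97.1 to 76.3%.

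**A perfect ID NOW** with no difference in spectrum (Accula 90% and 98%, prevalence 20%, same shares): sensitivity and specificity stay at 90% and 98%; PPV goes from 91.8 to 99.4% and NPV from 97.5 to 71.0%.

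**The case against.** - **Pooling is inferred.** This is true: the plan never says the cohorts are pooled. But with one total, one set of parameters and no stratification, pooling is the only analysis it describes.
- **Enrolling known positives is normal.** It is a reasonable way to obtain enough positives, and the concern does not oppose it. The defect is the unstated mix without separate reporting.
- **The mix may be small.** Ten known positives would lower apparent specificity only from 95.6% to 93.1%, or from 96.4% to 94.8% under maximal dependence. The plan sets no cap, so the size of the effect is open.
- **The bias does not always count against Accula.** Apparent sensitivity, the one parameter the Purpose section names, rises in the base case and in every check but one, where it is nearly flat. PPV usually rises as well. This stands: pooling can flatter Accula on some parameters while penalising it on others.
- **The root cause is the imperfect comparator.** This is largely so for specificity, and stratifying does not remove it: with no known positives at all, apparent specificity is 95.6% at 10% prevalence and 89.4% at 30%. But PPV and NPV would depend on the mix even with a perfect comparator, and the Background rules out a perfect ID NOW.
- **Existing PCR results are identifiable at discrepancy review, and cohort may be recoverable from other records.** Possibly, for staff with access. The plan does not exclude these fields, but it neither lists them nor uses the results in the calculation.
- **No decision threshold is set, so little depends on the figures.** The Purpose section speaks only of potential use. Even so, these four parameters are the main clinical-specimen comparison and carry the stated prediction.

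**Conclusion.** The concern holds and needs correcting before analysis. As written, the plan yields four parameters whose values depend on a recruitment mix it does not state, and which do not describe rapid-order patients alone.

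With 50 known positives in 100, the base case loses 18.4 points of apparent specificity (95.6% to 77.2%) and 7.4 points of NPV (98.2% to 90.8%) with both assays unchanged. Apparent specificity falls in every scenario with an imperfect ID NOW. NPV falls in all except maximal dependence. Apparent sensitivity mostly rises, and PPV has no fixed direction.

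The existence of the problem rests on the plan's text and its own description of ID NOW. The size rests on assumed accuracies, prevalence and mix, none of which the plan gives.

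**What to change.** 1. Add three columns to the spreadsheet: cohort (rapid-order or PCR-confirmed), enrolling PCR result, and days since that PCR.
2. State the number enrolled in each cohort.
3. Show the Accula-by-ID NOW 2x2 table for each cohort.
4. For the rapid-order cohort, report all four parameters, labelled as agreement with ID NOW.
5. For the PCR-confirmed cohort, report the proportion each assay detects, with days since PCR. Give no specificity, PPV or NPV, because nobody in it was enrolled as uninfected.
6. Do not report specificity, PPV or NPV on the pooled 100.

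The cost is three non-identifying columns and a stratified table, with no extra swabs or tests. Precision is lost. Under the base assumptions, a rapid-order cohort of 50 has about 5 Accula positives (3.384 + 2.016 = 5.4), and a PPV of 3/5 has an exact (Clopper-Pearson) 95% interval of 15% to 95%. If all 100 were rapid-order, 7/11 would give 31% to 89%. Sensitivity in that cohort of 50 would rest on about 4 ID NOW positives (3.384 + 0.816 = 4.2); the detection proportions in the PCR-confirmed cohort partly make up for this. The rapid-order figures remain agreement with an imperfect comparator and should be described that way.

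### Infections missed by both assays are scored as Accula true negatives, even in patients enrolled as PCR-positive, and confirming only the disagreements leaves this uncorrected

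*Combined protocol and SAP*

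**What the plan says.** Two kinds of patient enter the study. One has an order for rapid testing. The other is described in Methods: "We will also include patients who have been confirmed positive for COVID-19 by PCR". For the second kind, "two additional swabs will be collected: one for the ID NOW and one for the Accula test"; no repeat PCR is planned.

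Confirmation is described once, in Methods: "If there is a discrepancy between the ID NOW and Accula test results, an additional specimen (nasal) will be collected from the patient", with the limits "if possible (i.e. if the patient remains in-house) to confirm the COVID-19 results (unless the PCR results are already available". The test used must be better than either assay: "This additional test must be more sensitive than POCs". The exception for existing PCR results belongs to the rule for disagreements. Nothing sends an agreeing pair for confirmation or checks it against a PCR result already on file.

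The analysis is one sentence in Data Management and Analysis: "The following test parameters for the Accula will be calculated using the ID NOW as a comparator: sensitivity, specificity, positive-predictive value, negative predictive value". The same section lists what goes into the spreadsheet: the ID NOW result, the Accula result, and the Roche or send-out result if one was run. The PCR result that qualified a patient for enrolment is not on that list. The plan does not say how a confirmatory result enters any calculation.

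The Background describes the comparator: "While this assay has a high positive predictive value, the sensitivity and negative predictive value are low". It gives no figures.

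**The concern.** With the ID NOW as comparator, every pair negative on both assays is an Accula true negative and adds to specificity and NPV. If the patient is infected, that is an error, and because the pair agrees, the confirmation rule never reaches it. In the PCR-confirmed group the scoring goes against the study's own entry criterion: a patient enrolled as positive and missed by both assays is counted as correctly negative.

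Using PCR to settle the disagreements does not cure this. It reclassifies infections missed by one assay and leaves those missed by both where they were.

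Low sensitivity and low NPV are the stated weaknesses of the ID NOW. The Purpose section ties wider use of the Accula to comparable or superior parameters, sensitivity included. Two assays that fail in the same patients would look good against each other, and the infections that decide those two parameters would be out of sight.

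**Working it through.** The plan's only design figure is its target of 100 patients. It comes without prevalence, expected accuracy or precision, so there is no calculation to reproduce. What follows tests direction by algebra and size on assumed inputs.

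**Notation.** D is true infection, A the Accula result, I the ID NOW result, and n(...) the expected count in a cell.

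**Formulas for the Accula**
- NPV as planned = n(A-,I-) / n(A-)
- NPV with disagreements resolved by PCR = [n(A-,I-) + n(D-,A-,I+)] / n(A-)
- True NPV = n(D-,A-) / n(A-)
- PCR-resolved sensitivity = TP/(TP+FN), with TP = n(A+,I+) + n(D+,A+,I-) and FN = n(D+,A-,I+)

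**Direction**
- Planned minus true NPV = [n(D+,A-,I-) - n(D-,A-,I+)] / n(A-). It is positive only if shared misses outnumber ID NOW false positives among Accula negatives.
- Resolved minus true NPV = n(D+,A-,I-) / n(A-), which is never negative.
- Resolved sensitivity drops shared misses from FN and never loses a true positive, so it cannot be below the truth. The same holds for the ID NOW.
- The last two lines assume that every disagreement is confirmed, and correctly.

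A grid of 5,625 assumed scenarios (infected share 5-60%, sensitivities 60-95%, specificities 97-100%, errors from independent to maximally dependent) agrees. Resolved NPV and resolved sensitivity were below the truth in none. Planned NPV was below the truth in 1,875, all with imperfect ID NOW specificity. These counts reflect the grid chosen and are not probabilities.

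**Size: assumed inputs.** 60 rapid-order patients at 20% prevalence (12 infected, 48 not) and 40 PCR-confirmed patients, all taken as still infected: 52 infected in total. Among infected: both detect 70%, Accula only 10%, ID NOW only 5%, both miss 15%. No false positives.
- Counts: 36.4 both positive, 5.2 Accula only, 2.6 ID NOW only, 7.8 missed by both (6 of these are enrolled PCR-positives).
- Accula negatives: 48 + 7.8 + 2.6 = 58.4.
- NPV as planned: 55.8/58.4 = 95.5%. True: 48/58.4 = 82.2%. Excess: 7.8/58.4 = 13.4 points.
- PCR-resolved Accula sensitivity: 41.6/44.2 = 94.1%; true 41.6/52 = 80%.
- PCR-resolved ID NOW sensitivity: 39/44.2 = 88.2%; true 39/52 = 75%.
- Ratio of detections, Accula to ID NOW: 41.6/39 = 1.067, with or without the shared misses.

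**Varying the unknowns.** The shared-miss share is varied at the expense of the both-detect share; the 60 rapid-order patients are kept. Entries are planned NPV, true NPV, and the excess in points.

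| PCR-confirmed patients | 5% shared misses | 15% | 20% |
|---|---|---|---|
| 0 | 98.8, 97.6 (1.2) | 98.8, 95.2 (3.6) | 98.8, 94.1 (4.7) |
| 20 | 96.9, 93.8 (3.1) | 97.1, 88.2 (8.8) | 97.1, 85.7 (11.4) |
| 40 | 95.1, 90.2 (4.9) | 95.5, 82.2 (13.4) | 95.7, 78.7 (17.0) |

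The first row holds for any number of rapid-order patients at this prevalence. At 30% prevalence, 100 rapid-order patients and 15% shared misses, planned NPV is 74.5/76 = 98.0% against 70/76 = 92.1%.

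**When the planned NPV stops being too high.** With no Accula false positives, the break-even is as many ID NOW false positives as shared misses. The ID NOW PPV is then (its sensitivity) / (its sensitivity + shared-miss share):
- 5% shared misses: 0.85/0.90 = 94.4%
- 15%: 0.75/0.90 = 83.3%
- 20%: 0.70/0.90 = 77.8%

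Below those values the planned NPV is too low. One such case: 100 patients, 20% infected, Accula sensitivity 90% and specificity 99%, ID NOW 80% and 98%, independent errors. Planned NPV is 96.1% against a true 97.5%.

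**The case against.** Several objections stand and limit the point.

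- **Cause.** A reader might infer that the discordant-only rule creates the false true negatives. It does not. The ID NOW comparator does, and would still do so if every pair had a PCR result. The confirmation rule only fails to correct it.
- **Direction.** A reader might infer that the planned NPV must be too high. The break-even above shows otherwise. The Background's high PPV and low sensitivity point towards inflation, but without figures they do not settle it.
- **Discrepant analysis.** A reader might infer that the study will report PCR-resolved sensitivity. No sentence says so; the further specimen is there to confirm results. The resolved figures show what would happen if confirmatory results were put to that use. Sensitivity against the ID NOW, the planned figure, leaves shared misses out altogether and can err either way.
- **Enrolment PCR as truth.** The interval from qualifying PCR to study swabs is not stated. A double negative may reflect viral clearance, so not every one is a missed infection. That argues for recording the date. It does not justify counting the patient silently as a true negative.
- **Shared misses are not always invisible.** Some rapid-order patients may have a PCR result already. The plan consults it only when the pair disagrees.
- **The purpose is comparative.** The ratio of detections is unaffected by shared misses. But the plan reports absolute sensitivity and NPV, and those are affected.

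**Conclusion.** The scoring is wrong as written for PCR-confirmed patients who are still infected and are missed by both assays: they count as Accula true negatives, and nothing in the plan brings in the PCR result that would show it. In rapid-order patients the same error occurs, mostly unseen.

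The planned NPV is likely, not certain, to be too high. If PCR resolves only the disagreements, and does so completely and correctly, NPV and both sensitivities cannot fall below their true values and exceed them whenever any infection is missed by both.

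The documents do not fix the size. On the stated assumptions the NPV excess is about 1-5 points with no PCR-confirmed patients and about 5-17 with 40. The plan gives no number for that group. The larger range must not be read as the error in a clinical NPV: it comes from a sample to which known positives were added. Over the same 5-20% of shared misses, resolved Accula sensitivity is overstated by 4.7 points (90/95 = 94.7% against 90%) to 18.8 points (75/80 = 93.8% against 75%).

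**What to change.** 1. **PCR-confirmed group.** Enter the qualifying PCR result and its date in the spreadsheet. Report each assay's positive agreement with that PCR over all pairs, agreeing pairs included. Never count a both-negative pair in this group as a true negative in specificity or NPV. Show results by interval from PCR to study swab, and note that a late double negative may reflect clearance.
2. **Rapid-order patients, reported separately.** Enter any PCR result already available, whether or not the pair agrees. Report positive and negative percent agreement with the ID NOW. Add the paired ratio and the paired difference of confirmed detections, with 95% intervals. Double positives are treated as true, which the stated high ID NOW PPV supports; say so. Some disagreements will stay unconfirmed because the patient has left, so show bounds with those pairs counted each way.
3. **Labelling.** Do not present rapid-order NPV or PCR-resolved sensitivity as accuracy figures. If PCR-resolved figures are shown, call them upper bounds.

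The cost is two spreadsheet columns and revised analysis wording, with no new swabs or tests. Data shared outside the testing team need only the interval in days, not the date. The downside is that no absolute sensitivity or NPV can be claimed for rapid-order patients, and some figures become less favourable.

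### The plan lets the Accula operator know a patient's ID NOW result before the Accula result is recorded

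*Combined protocol and SAP*

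**What the plan says.** **Who runs what (Methods).** Trained microbiology technologists and technicians run ID NOW. For Accula, "Testing personnel for the Accula assay will consist of a lead medical laboratory scientist and the technical director of the microbiology laboratory".

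**Who enters the data (Data Management and Analysis).** "The lead technologist or technical director will enter the ID NOW results into the secure data file using the ID NOW hardcopy reports". The Accula result, and any Roche or send-out result, goes into the same spreadsheet under the same barcode. Only the lead technologist and the technical director can open that file. The ID NOW printouts are kept in a binder in the laboratory.

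**Timing (Background and Methods).** "The ID NOW COVID-19 assay will continue to be performed STAT", and it gives a result within 15 minutes. Accula takes up to 30 minutes. It is run immediately if personnel are available; if not, the swab may be held for two hours at room temperature, or at 2-8°C "for up to 24 hours prior to testing on the Accula".

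**How Accula is run (Methods).** "The protocol for testing will strictly follow the manufacturer's instructions". Those instructions are cited by link and not reproduced. The only repeat runs described are for "precision (reproducibility) by repeating select specimens with different users and on different analyzers".

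**What depends on the result.** Accula sensitivity, specificity, PPV and NPV are all calculated against ID NOW (Data Management and Analysis). Disagreement also starts the confirmation step in Methods: "If there is a discrepancy between the ID NOW and Accula test results, an additional specimen (nasal) will be collected from the patient", where possible and "unless the PCR results are already available".

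**The concern.** In a paired comparison of two tests, each result should be fixed without knowledge of the other. Otherwise a doubtful reading, or a choice to run a sample again, can be influenced by the answer already on paper. Here one named role is both an Accula operator and a possible transcriber of the comparator, and the comparator will often be available first. The plan sets no order of reading or entry, no masking and no locking of results.

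The comparison with ID NOW is the study's only accuracy analysis, and its outcome may support wider use of Accula. It also decides which patients get a confirmatory test. A call moved towards ID NOW removes a discordant pair, and a call moved away from it creates one. Either would affect the confirmation data as well as the four parameters, except where a PCR result already exists.

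**Working it through.** The plan gives no figure to reproduce here. The 100 patients in Sample Size and Duration of Study come without an assumed prevalence, agreement, margin or power, and this point does not dispute that number.

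**Step 1. Can the operator have access to the ID NOW result?** Yes. The technical director appears by title both in the Accula testing sentence and in the ID NOW transcription sentence. The other titles differ (lead medical laboratory scientist in one place, lead technologist in the other). They may be the same person, but the point does not need that.

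**Step 2. Can the ID NOW result exist first?** Yes. If both tests start together, ID NOW reports within 15 minutes and Accula within 30. If the Accula swab is stored, the gap can approach 24 hours.

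**Step 3. Does any rule prevent the operator from seeing it?** No such rule appears in Methods or in Data Management and Analysis. Both were searched for masking, reading order, entry order, result locking, and handling of invalid or repeat Accula runs.

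**Step 4. Is there discretion to be influenced?** The documents do not settle this. Background mentions a lateral-flow step and Methods mentions analyzers, but neither says whether a person or the device makes the call. The manufacturer's instructions may settle both the call and the repeats, but they are not in the documents. The plan does not say how specimens are chosen for the precision repeats or which run enters the accuracy analysis.

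**Step 5. Scale of a single changed call.** These inputs are assumptions, because the documents give no expected number of positives. With n ID NOW positives among 100 patients, one changed Accula call in an ID NOW-positive patient moves positive agreement by 100/n points:

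| Assumed n | Calculation | Change in positive agreement |
|---|---|---|
| 20 | 100/20 | 5.0 points |
| 30 | 100/30 | 3.3 points |
| 40 | 100/40 | 2.5 points |
| 50 | 100/50 | 2.0 points |

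The change is upward if the call moves to match ID NOW and downward if it moves away. For comparison, if 18 of 20 ID NOW positives were Accula positive (90.0%), the exact 95% interval would be 68.3 to 98.8%. One changed call (19/20 = 95.0%) lies well inside it. The table shows how sensitive the estimate is to one call. It is not evidence that any call would change.

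**The case against.** The strongest reply is that harm needs operator discretion, and the documents show none. Accula testing must strictly follow the manufacturer's instructions, which may fix both the call and the handling of repeats. Different staff run ID NOW, immediate Accula testing is the first path, and the transcription sentence is compatible with entering ID NOW after Accula is finished. The only repeats described are for precision, listed separately from accuracy. All of this stands, and it is why the consequence is conditional. It does not supply the missing rule: separate staff limits who runs ID NOW, not who sees its result, and nothing in the plan says that the instructions require reading without knowledge of the comparator.

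A reader might go further and infer that agreement will be inflated. The documents do not support a direction. Background describes ID NOW as having low sensitivity and negative predictive value, and Predicted Results expects Accula to do at least as well. An operator holding those views might accept a doubtful Accula positive against a negative ID NOW, which would lower agreement and create a discordant pair.

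A reader might also infer that the operator will have seen the ID NOW result, or that a repeat may replace a patient's accuracy result. The text states neither. It leaves both open.

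**Conclusion.** The gap holds: as written, the plan allows an Accula operator to know the comparator result before making, recording or repeating a call. That follows directly from the named roles and the timing, without any assumption.

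That bias results does not follow. It rests on the unverified condition that the call or the decision to repeat involves some discretion. Direction and size are unknown, and the effect may be zero. The 5-to-2-point range per changed call depends wholly on an assumed 20 to 50 ID NOW positives. One such change would be within sampling error, but a systematic influence would not shrink with more patients.

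This is a point for the sponsor to consider, not a demonstrated error in the results. It merits action because the safeguard costs almost nothing and cannot be recovered once an operator has seen the comparator.

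**What to change.** Add a few sentences to Methods and Data Management and Analysis:

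1. For each patient, record and time-stamp the Accula result before its operator views that patient's ID NOW report.
2. Transcribe the ID NOW hardcopy only after that Accula entry is locked.
3. Compare the two results at once, so that the discrepancy step is not delayed.
4. Use the first valid Accula run in the accuracy analysis, and keep the precision repeats separate.

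The cost is a time-stamp column and slightly less flexible data entry. No extra staff, swabs or tests are needed, the target of 100 patients stays, and STAT reporting of ID NOW is unchanged.
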